## Inhibitor Subgroups

Patients developing a positive inhibitor after exposure to rFIXFc will be included in Inhibitor Subgroup. Within this subgroup, there are several further classifications:

1. Patients with high-titer inhibitors, defined as in Section 5.2.4
2. Patients with low-titer inhibitors, defined as Section 5.2.4, that meet the below clinically meaningful criteria
3. Patients with low-titer inhibitors that do not meet the below clinically meaningful criteria

The delineation of clinically meaningful will be performed on a case-by-case basis via medical adjudication prior to the final analyses, based upon the data available for the analysis. This assessment will take account of relevant clinical factors, including but not limited to:

- Entry to the ITI regimen
- Any bypassing or immunomodulatory agents received up to 4 weeks before inhibitor development and any time after
- Withdrawal from the study due to complications assessed as related to inhibitor development
- Any SAE of a bleeding event up to 4 weeks before inhibitor development or any time after
- A pattern of non-serious treated bleeding events which require a change in study drug (rFIXFc) regimen

By definition, all high-titer inhibitors are clinically meaningful, as patients with high-titer inhibitors must either enter the ITI sub-study or withdraw.

## ITI Subgroup

The ITI Subgroup is defined as all patients who consent to and initiate the ITI treatment regimen (see Section 3.1.2.3). This set will be described in the disposition table and all analyses and listings of data from the ITI regimen will be presented for this population when applicable.

### 5.2.6. End of Study

The end of the study (EOS) will occur after at least 20 patients have reached at least 50 EDs with rFIXFc. Once this milestone has been achieved, all ongoing study patients will return to the study center for their final visits.

## 5.3. Treatment Regimens for Analysis

For the purpose of analysis, the treatment regimen means the actual treatment regimen(s) that the patient follows over the course of the study (i.e., not necessarily the regimen they started on). For example, a patient who starts the study on the episodic regimen and switches to a prophylactic regimen will appear in the summaries of both the episodic and the prophylactic regimens based on the time he spent in the respective regimens.

	Statistical Analysis Plan	Final v1.0
---	----------------------------------	-------------------

### 5.3.1. Start Date and Time of the First Treatment Regimen

The start date and time of the first treatment regimen is defined as either:

- The date and time of the first rFIXFc dose for patients beginning on a prophylactic treatment regimen, as per the treatment assignment eCRF data.
- The date and time 120 hours after the date and time of the baseline PK dose for patients beginning on an episodic treatment regimen, as per the treatment assignment eCRF data.

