The Baseline IR Visit assessments should be performed as soon as practicable once all eligibility criteria have been met and the subject has been enrolled. The Baseline IR Visit activities (Section 4.2.1) may be completed on the same day as Screening, or they may be completed as part of a separate visit or at an unscheduled visit. Baseline IR assessments must be performed when the subject is in a non-bleeding state, after at least a 72 hour washout. Eligible subjects will report to the study site for administration in the clinic of the Baseline IR Visit dose of 50 IU/kg by actual potency (see the Directions for Handling and Administration [DHA] and Section 10.1.1 of this protocol for further information on actual potency dosing). The dose will be delivered via a slow push IV injection over several minutes, at a rate of administration determined by the subject's comfort level. Subjects will be required to complete the assessments according to Section 4.2.1, including collection of FIX activity samples for the calculation of incremental recovery.

Bleeding episodes that occur prior to meeting all eligibility criteria should be treated with commercially available rFIXFc. If a subject requires more than 3 injections of commercially available rFIXFc prior to confirmation of eligibility, the subject will be considered a screen failure. In countries where rFIXFc is not yet commercially available, any bleeding episode that occurs prior to meeting eligibility criteria should be treated with another FIX concentrate and the subject will be considered a screen failure. After meeting eligibility criteria, all bleeding episodes should be treated with rFIXFc study drug. The Baseline IR Visit may be delayed until the subject is in a non-bleeding state and a 72-hour washout period may be safely performed.

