9.1.4. Baseline Incremental Recovery

Baseline IR assessments described in Section 4.2.1 should be performed as soon as practicable once all eligibility criteria have been met and the subject has been enrolled. The Baseline IR

CONFIDENTIAL

The information contained herein may not be used, disclosed, or published without the written consent of Bioerativ
Therapeutics Inc

Visit activities may be completed on the same day as Screening, or they may be completed as a part of a separate visit or at an unscheduled visit. They must be performed when the subject is in a non-bleeding state and after at least a 72 hour washout. The Baseline IR Visit may be delayed until the subject is in a non-bleeding state.

The sample for predose FIX activity does not have to be collected if the subject has not received any dose of any product containing FIX (including commercially available rFIXFc or a blood product transfusion) prior to the dose for the baseline IR assessment.

For the Baseline IR measurement, a dose of 50 IU/kg will be given in the clinic as an IV injection. The *actual* potency of rFIXFc must be used to calculate the units and volume of rFIXFc infused for the Baseline IR Visit dose (see the DHA and Section 10.1.1 of this protocol).

For the baseline IR assessment, blood samples will be taken predose within 30 minutes prior to the start of the injection and postdose at 10 (± 5) minutes after the end of the rFIXFc injection for assessment of IR, measured by the one-stage aPTT clotting assay. According to the local standard of care, an IV access device may be offered to facilitate sample collection. The IV access device must not be flushed with heparin between injection of rFIXFc and the collection of the samples.

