### 5.3.3. Treatment Regimen Changes

In the following sections, new treatment regimen refers to the regimen to which the patient has changed, and the previous treatment regimen refers to the regimen immediately before the new treatment regimen. The start date and time of the new treatment regimen and the end date and time of the previous treatment regimen are defined in the following scenarios:

- From an episodic regimen to a prophylactic regimen: The prophylactic regimen starts at the date and time of the first prophylactic dose in the prophylactic regimen. The episodic regimen ends 1 minute before that. If the time of the first prophylactic dose in the prophylactic regimen is not available, the prophylactic regimen will start at 00:01 on the day of the first prophylactic dose in the prophylactic regimen, and the episodic regimen will end at 23:59 on the day prior to that.
- From a prophylactic regimen to an episodic regimen: The prophylactic regimen ends at the date and time of the last prophylactic dose in the prophylactic regimen. The episodic regimen starts 1 minute after that. If the time of the last prophylactic dose in the prophylactic regimen is not available, the prophylactic regimen will end at 23:59 on the day of the last prophylactic dose in the prophylactic regimen, and the episodic regimen will start at 00:01 on the next day.
- From an episodic regimen to an ITI regimen: The ITI regimen starts at the date and time of the first ITI dose in the ITI regimen. The episodic regimen ends 1 minute before that. If the time of the first ITI dose in the ITI regimen is not available, the ITI regimen will start at 00:01 on the day of the first ITI dose in the ITI regimen, and the episodic regimen will end at 23:59 on the day prior to that.
- From a prophylactic regimen to an ITI regimen: If there is no prophylactic dose on the day of the treatment regimen change recorded in the eCRF, the ITI regimen starts at

	Statistical Analysis Plan	Final v1.0
---	----------------------------------	-------------------

00:01 on the day of treatment regimen change, and the prophylactic regimen ends at 23:59 on the day prior to the day of treatment regimen change. If there is a prophylactic dose on the day of treatment regimen change, the ITI regimen starts 1 minute after that prophylactic dose, and the prophylactic regimen ends on the date and time of that prophylactic dose.

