#### **5.4.2. Efficacy Period**

The efficacy period will be used for the evaluation of efficacy and health outcome endpoints. For a patient to have an evaluable efficacy period over the duration of study, he must have at least 1 day of treatment for an episodic regimen or at least 2 prophylactic injections for prophylactic regimens.

The start and end, and the total duration of the efficacy period for a given treatment regimen is the same as the start and end, and the total duration of that treatment regimen defined in Section 5.3.4 with the exceptions described in the following two subsections. The start of the efficacy period for each patient is the start of their first treatment regimen and the end is the end of their last.

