##### **5.4.2.1. Adjustments Due to Surgical/Rehabilitation Periods**

For analysis purposes, the efficacy period for a given treatment regimen will be adjusted for all surgical/rehabilitation periods (major and minor). The start and end of the efficacy period for a given treatment regimen are adjusted as follows:

	Statistical Analysis Plan	Final v1.0
---	----------------------------------	-------------------

- For patients on a prophylactic regimen before the start of a surgical/rehabilitation period, the efficacy period for the prophylactic regimen continues up to the last dose (for prophylaxis or bleeding) before the start of the surgical/rehabilitation period.
- For patients on the episodic regimen before the start of a surgical/rehabilitation period, the efficacy period for the episodic regimen continues up to 1 minute before the start of a surgical/rehabilitation period.
- For patients on a prophylactic regimen following the end of a surgical/rehabilitation period, the efficacy period for the prophylactic regimen starts or re-starts at the first prophylactic dose following the end of the surgical/rehabilitation period.
- For patients on the episodic regimen following the end of a surgical/rehabilitation period, the efficacy period for the episodic regimen starts or re-starts at 00:01 on the day following the end of the surgical/ rehabilitation period.

Start and end dates/times for the efficacy period for given treatment regimens and treatment regimen changes will be adjusted for each surgery (major or minor) as necessary.

For patients on a prophylactic regimen before the start of a surgical/rehabilitation period, the interval of time between the last dose before the surgical/rehabilitation period and the start of the surgical/rehabilitation period will not be attributed to the efficacy period for the prophylactic regimen. By definition, there should not be any treated bleeding episodes in this interval of time.

For patients on a prophylactic regimen following the end of a surgical/rehabilitation period, bleeding episodes that occur after discharge from a rehabilitation facility but before the next prophylactic dose will be attributed to the surgical/rehabilitation period and hence not counted towards the annualized bleeding rate (ABR).

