#### **5.4.2.2. Adjustments Due to Large Injection Intervals**

For analysis purposes, the efficacy period will also be adjusted to account for large intervals between injections resulting from missing data. A large interval is defined as >28 days between any 2 adjacent rFIXFc injections within a prophylactic treatment regimen and any such intervals will be removed from the efficacy period. The efficacy period prior to each such interval will end at the time of the first injection of this interval and restart (or start if it is the first interval of a treatment regimen) at the time of the second injection of this interval. The efficacy period will be adjusted for each identified interval that is not within a surgical/rehabilitation period. This algorithm applies only to prophylactic regimens and no adjustment for large injection intervals will be made for episodic treatment regimens.

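### For prophylaxis starters, SAP 5.3.1 opens the efficacy period at the first rFIXFc dose given for any reason, while SAP 5.3.3 and 5.4.2.1 use the first prophylactic dose

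*SAP*

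**What the plan says.** SAP 5.3.1 gives two rules for the start of a child's first regimen, chosen by the regimen recorded on the treatment assignment form.

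- Prophylaxis starters: "The date and time of the first rFIXFc dose for patients beginning on a prophylactic treatment regimen".
- Episodic starters: "The date and time 120 hours after the date and time of the baseline PK dose for patients beginning on an episodic treatment regimen".

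SAP 5.4.2 carries this into efficacy: "The start of the efficacy period for each patient is the start of their first treatment regimen". The ABR (7.4.3) and annualized consumption (6.6.1.4) both divide by the days in that period.

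Elsewhere the SAP ties prophylaxis to a prophylactic dose. On a switch from episodic treatment, 5.3.3 says: "The prophylactic regimen starts at the date and time of the first prophylactic dose in the prophylactic regimen". After surgery, 5.4.2.1 says: "the efficacy period for the prophylactic regimen starts or re-starts at the first prophylactic dose following the end of the surgical/rehabilitation period".

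The protocol allows a first study-drug dose that is not prophylactic. Section 7.3.1 says: "After meeting eligibility criteria, all bleeding episodes should be treated with rFIXFc study drug". It also lets the baseline recovery visit wait until the child is not bleeding and a washout is safe. Section 9.1.4 describes the recovery dose: "For the Baseline IR measurement, a dose of 50 IU/kg will be given in the clinic as an IV injection".

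SAP 6.6 states that PK doses serve neither to prevent nor to treat bleeding, and leaves them out of consumption. SAP 6.6.1.4 describes the efficacy period as excluding PK assessments. Section 5.4.2 contains no such exclusion, and 5.4.6 says no PK period is defined.

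**The concern.** One regimen column is opened by two different events, depending on how the child entered it. Switchers contribute time from their first prophylactic dose. Starters contribute time from whatever rFIXFc dose came first. If that dose was for recovery or for a bleed, the stretch before the first prophylactic dose is credited to prophylaxis.

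Two secondary endpoints are touched. The prophylaxis ABR picks up days, and possibly bleeds, that precede prophylaxis. Annualized consumption keeps those days in its denominator while the recovery dose is removed from its numerator, so the two parts of the ratio cover different time. With about 30 children enrolled and ABR summarized per child, including a zero category, one early bleed can move a child out of that category.

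**Working it through.** The documents give no figure for this effect, so there is nothing to reproduce. The steps below apply the SAP's own formulas under both start rules.

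**Inputs**
- SAP 7.4.3: ABR = bleeds / days × 365.25.
- SAP 6.6.1.4: annualized consumption = total IU/kg / days × 365.25, with PK doses excluded (SAP 6.6).
- Protocol 7.3.2 and 10.2.2.2: recommended starting prophylaxis of 50 IU/kg weekly.
- SAP 5.4.2.2, the only rule that trims the gap: "A large interval is defined as >28 days between any 2 adjacent rFIXFc injections within a prophylactic treatment regimen". Such intervals are removed.
- Assumptions: T = days from first prophylactic dose to last dose, taken as 343 (49 weekly intervals, so 50 doses), 182 or 91. g = days from first rFIXFc dose to first prophylactic dose, taken as 7, 14 or 28. The documents give no values for g.

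**ABR, no bleed in the gap.** The SAP rule divides the same bleeds by T + g instead of T, so a non-zero ABR falls by g / (T + g):

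| T | g = 7 | g = 14 | g = 28 |
|---|---|---|---|
| 343 | 2.0% | 3.9% | 7.5% |
| 182 | 3.7% | 7.1% | 13.3% |
| 91 | 7.1% | 13.3% | 23.5% |

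**ABR, one bleed in a 7-day gap**
- No later bleeds, T = 343: 0 from the first prophylactic dose; 1 / 350 × 365.25 = 1.04 under 5.3.1.
- No later bleeds, T = 91: 0 versus 1 / 98 × 365.25 = 3.73.
- One later bleed, T = 343: 1 / 343 × 365.25 = 1.06 versus 2 / 350 × 365.25 = 2.09.
- One later bleed, T = 91: 1 / 91 × 365.25 = 4.01 versus 2 / 98 × 365.25 = 7.45.

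**Consumption, first dose is the recovery dose, 50 IU/kg weekly afterwards**
- T = 343, g = 7: 50 doses × 50 = 2500 IU/kg. From the first prophylactic dose, 2500 / 343 × 365.25 = 2662. Under 5.3.1 with the PK dose removed, 2500 / 350 × 365.25 = 2609.
- T = 91, g = 28: 14 doses × 50 = 700 IU/kg. 700 / 91 × 365.25 = 2810 versus 700 / 119 × 365.25 = 2149.
- If the recovery dose were counted along with its days (T = 343, g = 7), 2550 / 350 × 365.25 = 2661, almost the same as 2662. The understatement comes from the mismatch between numerator and denominator.

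**Limits**
- The 28-day cut applies to each pair of adjacent injections. Several non-prophylactic doses could leave a longer total stretch.
- Average weekly dose and dosing interval (SAP 6.6.1.3) are unaffected, because they use only intervals between prophylactic doses.

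**The case against.** **The recovery dose may act as the first weekly dose.** It is 50 IU/kg, the recommended weekly amount, and protocol 5.3 predicts that weekly dosing at this level keeps troughs above 1% in 99% of pediatric subjects. This stands in part. A reader might infer that all the gap time is unprotected, and the documents do not support that. But the SAP does not say the recovery dose counts as prophylaxis, and 6.6 treats it as non-preventive.

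**Few children may be affected.** SAP 5.3 defines regimen by what the child actually follows, so a child treated only for bleeds over some weeks would normally be an episodic starter and enter prophylaxis through 5.3.3. This stands. The documents give no count of recorded prophylaxis starters with a real gap.

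**The bias has no fixed sign.** A reader might infer that the rule inflates the prophylaxis ABR. It does so only if a bleed falls in the gap and outweighs the added days. Sizing the effect from protocol 5.1.1 does not settle this: its 3 to 4 per year on prophylaxis are spontaneous bleeds, while its figure of about 20 per year on episodic treatment covers bleeding episodes generally.

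**The bleed treated by the first dose may not count.** Under SAP 5.2.4 an episode begins at its first sign, which precedes that dose and therefore the clock. The SAP does not say whether such a bleed enters the numerator, so it cannot be assumed to.

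**The endpoints are secondary and descriptive.** The primary endpoint is inhibitor development and no regimens are formally compared. This limits the importance of the point but does not reconcile the two start rules.

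**Conclusion.** The inconsistency is real, and no section of either document resolves it. Its effect is bounded and usually small. It is nil when the first dose is prophylactic, and no single injection interval longer than 28 days survives 5.4.2.2. At 343 days of prophylaxis, a bleed-free gap of 7 to 28 days lowers a non-zero ABR by 2.0% to 7.5%. A single bleed in a 7-day gap, with none later, moves a child from 0 to 1.04, or to 3.73 with only 91 days. Consumption has a definite direction when a recovery dose opens the period: it is understated, by 2.0% in the 7-day, 343-day case. These sizes rest on assumed gaps, follow-up and bleed counts.

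A reader might also take the words of 5.3.1 to include commercially available rFIXFc given before enrollment. Protocol 16.2.1 limits efficacy data to the time from the first study-drug injection, so that reading is not supported.

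**What to change.** In SAP 5.3.1, start the prophylaxis efficacy period at the first dose whose recorded reason is prophylaxis, as 5.3.3 and 5.4.2.1 already do. Align 6.6.1.4 so that the doses and the days cover the same time.

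List bleeds, days and doses before that point as a separate pre-prophylaxis interval, outside both the prophylaxis and the episodic ABR columns. Moving them into the episodic column would be unsound. Section 5.4.2 asks for only 1 day of episodic treatment, so one bleed in 7 days would give an ABR of 365.25 / 7, about 52, for a child never assigned to that regimen.

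If the sponsor intends the recovery dose to count as the first prophylactic dose when the next one follows within the prescribed interval, say so in 5.3.1 and then include that dose in consumption.

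The cost is a wording change and one date derivation. The reason for administration is already part of the dosing data (SAP 6.6). The downside is a few days of follow-up lost from the efficacy period for each affected child.

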- ^d Medical and surgical history includes any significant medical condition and/or any significant surgical histories, plus the following: HIV infection status (if positive, viral load, cluster of differentiation 4 [CD4] count, and platelets; based on laboratory results within the last 6 months), hepatitis B infection status, hepatitis C infection status, medication history, and any other congenital immunodeficiency. Medical history should also include any dosing with commercially available rFIXFc for bleeding episodes between 28 days prior to Screening and meeting all eligibility criteria.
- ^e After screening, physical examination should be performed at least annually; more frequent physical examinations may be performed at the Investigator's discretion, according to their standard of care.
- ^f Vital signs include blood pressure, pulse rate, respiratory rate, and temperature (°C). Postdose assessments following in-clinic injections should be taken approximately 10 minutes after the end of the rFIXFc injection.
- ^g Hematology includes white blood cell count and differential, red blood cell, hemoglobin, hematocrit, and platelet count.
- ^h Blood chemistry includes sodium, potassium, chloride, total protein, total bilirubin, gamma glutamyl transferase, aspartate aminotransferase, alanine aminotransferase, alkaline phosphatase, blood urea nitrogen, serum creatinine, and glucose.
- ⁱ Sample to be used to determine seropositivity at Screening, should subject be diagnosed with HIV, hepatitis B, or hepatitis C during the study.
- ^j Washout prior to sample collection for inhibitor and anti-rFIXFc antibody tests should be at least 72 hours (including prior to collection of the Screening sample, if there was prior dosing with FIX). Samples for anti-rFIXFc antibody testing will be collected at the same timepoint when any samples are collected for inhibitor testing, including confirmatory and unscheduled inhibitor tests. An unscheduled visit may be required to obtain samples to confirm a positive inhibitor test result.
- ^k See minimum criteria for enrollment, Section 8.3.
- ^l The predose sample collection for FIX activity, anti-rFIXFc antibody, and inhibitor testing are only required for subjects who received at least 1 dose of any product containing FIX, including commercially available rFIXFc or a blood product transfusion, prior to the dose for the baseline IR assessment.

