10.2.2.1. Episodic Treatment (Optional)

Once eligibility has been confirmed and the subject has been enrolled, the Investigator has the option to treat the subject episodically, until a prophylactic regimen is initiated. Dosing will be determined by the Investigator using [Appendix A](#) as a guideline. The duration of episodic treatment is at the Investigator's discretion and should be based upon the Investigator's treatment plan for the subject in accordance with the local standard of care. However, given global standards of care, it is expected that the prophylactic regimen will be initiated prior to or immediately following a third episode of hemarthrosis [[Berntorp 1995](#); [Manco-Johnson 2007](#); [MASAC 2007](#)]. The date of transition from episodic treatment to a prophylaxis regimen must be captured on the eCRF.

CONFIDENTIAL

The information contained herein may not be used, disclosed, or published without the written consent of Bioerativ
Therapeutics Inc

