10.2.3.2. Information to be Recorded for Bleeding Episodes

Subjects or their parent/caregiver must be issued with an EPD once eligibility has been confirmed and they have been enrolled; from that point forward, all data regarding bleeding episodes and injections administered for a bleeding episode for doses administered at the subject's home or at locations other than the study site must be entered into the EPD. The incidence of bleeding in this study will be obtained from EPDs, eCRFs, and medical records. If a subject has enrolled in the study, information from medical records on dosing and bleeding episodes treated with commercially available rFIXFc prior to the subject being issued with an EPD should be recorded in the eCRF, according to the eCRF Completion Guidelines.

It is recommended that subjects or parents/caregivers enter bleeding episode information into the EPD immediately after an injection.

The Investigators and Clinical Monitors will ensure that there is consistency in bleeding episode data between the subject's medical record, IXRS, source documents, EPD, and eCRFs. During the clinic visits and monthly telephone calls with the subject's parents/caregivers, the subject/parent/caregiver will be reminded about timely EPD completion and the Investigator will verify whether or not a bleeding episode has occurred, and was "spontaneous" or "traumatic" (Section 10.2.3.1).

If, following this discussion, the Investigator judges that the classification by the subject's parents/caregivers was incorrect, the Investigator will document it in the subject's medical records with the rationale for the new classification, and the eCRF, documenting the new classification of the bleeding episode according to the Investigator and whether or not the subject's parents/caregivers agreed with this new classification. With regard to dose changes, the Investigator's classification of spontaneous or traumatic will be used (if different from the classification recorded in the EPD by the parent/caregiver). Both spontaneous and traumatic bleeding episodes will be collected.

Information collected in the EPD will include, but not be limited to, the following:

- the type of bleeding episode (e.g., spontaneous, traumatic) and if related to sports activity or physical activity
- the date the bleeding event occurred
- the dose administered to treat the bleeding episode including any repeat doses
- the location of the bleed

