10.2.3.4. Procedure to Treat the Bleeding Episode

After meeting eligibility criteria, all bleeding episodes should be treated with rFIXFc study drug. Dosing calculations should be performed as described in the DHA and summarized in [Section 10.1.1](#) of this protocol.

Subjects and their parents/caregivers should be instructed to treat at the first sign of a bleeding episode and with a single dose of rFIXFc. Most bleeding episodes should resolve with a single dose of rFIXFc. See [Section 10.2.3.4](#) and [Appendix A](#) for rFIXFc dosing guidance.

- If the bleeding episode resolves with a single IV dose of rFIXFc, the subject will return to the schedule of dosing used prior to the bleeding episode.
- If the bleeding episode does not resolve within 48 hours with the single IV dose of rFIXFc, the subject's parents/caregivers should contact the Investigator for advice. Administration of a second dose of rFIXFc as follow-up treatment will be determined by the Investigator based on the subject's clinical condition. Once the bleeding event resolves, the subject will return to the rFIXFc dosing schedule used prior to the bleeding episode.
- If the bleeding episode does not resolve with 2 doses (initial and follow-up treatments) of rFIXFc, the subject's parents/caregivers should contact the Investigator for advice. A third dose of rFIXFc will be administered within 48 hours after the administration of the second dose of rFIXFc. The repeat dose may be at the same dose or a dose determined by the Investigator based on the subject's clinical condition. Once the bleeding event resolves, the subject will return to the rFIXFc dosing schedule used prior to the bleeding episode.
- If the bleeding event has still not resolved with 3 doses (initial and 2 follow-up treatments) of rFIXFc, the Investigator should consult with the Medical Monitor to determine if the subject should be withdrawn from the study. See [Section 11](#).

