### **Baseline Incremental Recovery Visit**

Baseline IR Visit assessments are performed as soon as practicable once all eligibility criteria have been met and the patient has been enrolled. The Baseline IR Visit activities may be completed on the same day as Screening, or they may be completed as a part of a separate visit or at an unscheduled visit. Samples for IR calculations are taken when the patient is in a non-bleeding state, after at least a 72 hour washout.

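### For children who start episodically, the efficacy clock opens only 120 hours after the baseline PK dose, so earlier treated bleeds are dropped and two cases have no usable start

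*SAP*

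**What the plan says.** SAP 5.3.1 gives two starts for a first regimen. For prophylaxis it is "The date and time of the first rFIXFc dose for patients beginning on a prophylactic treatment regimen". For episodic treatment it is "The date and time 120 hours after the date and time of the baseline PK dose for patients beginning on an episodic treatment regimen". SAP 5.4.2 carries these over as the start of the efficacy period, with exceptions only for surgery and for prophylactic injection gaps above 28 days. SAP 7.1, 7.4.3 and 6.6.1.4 then confine bleeding data, ABR and annualized consumption to that period.

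The baseline PK dose is given at the Baseline IR Visit, for which neither document sets a latest date. SAP 5.2.3 says: "Baseline IR Visit assessments are performed as soon as practicable once all eligibility criteria have been met and the patient has been enrolled". Protocol 7.3.1 says: "The Baseline IR Visit may be delayed until the subject is in a non-bleeding state and a 72-hour washout period may be safely performed". Treatment and recording do not wait for that visit. Protocol 10.2.3.4 says: "After meeting eligibility criteria, all bleeding episodes should be treated with rFIXFc study drug"; Protocol 7.3.1 has the same instruction directly before the sentence on delay. The diary is issued "once eligibility has been confirmed and they have been enrolled; from that point forward, all data regarding bleeding episodes" and off-site injections go into it (Protocol 10.2.3.2). Under Protocol 10.2.2.1 episodic treatment may begin at enrolment, and "it is expected that the prophylactic regimen will be initiated prior to or immediately following a third episode of hemarthrosis".

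**The concern.** A bleed soon after enrolment is treated with study drug and postpones the Baseline IR Visit. The postponement then places that same bleed, its dose and the surrounding days outside the efficacy period. Drug cover from the PK dose could justify setting aside the 120 hours after it, but not the time before it. The PK units themselves already leave consumption under SAP 6.6.

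Two cases have no workable rule:

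- **No PK dose.** The episodic regimen has no start time, and SAP 5.5 rules out imputation beyond its listed items.
- **Prophylaxis before PK dose plus 120 hours.** SAP 5.3.3 ends the episodic regimen before 5.3.1 starts it. The child's overall efficacy start (5.4.2) then falls after his prophylaxis start.

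ABR and consumption are secondary endpoints, reported by regimen. The patient-years in SAP 7.4.2 shrink too. SAP 7.4.8, which names no period of its own, may also lose these bleeds. They are among a child's first bleeds treated with study drug, and the episodic phase is optional, so few children contribute.

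**Working it through.** The plan gives no figure for this rule, so there is none to reproduce. The definitions come from the SAP. Delays, bleed rates and switch times are assumptions.

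**Time excluded.** Let D be the day of the PK dose and E the day of the first prophylactic dose, both counted from enrolment. The SAP excludes (D + 5)/E of the episodic time; removing only the 120 hours excludes 5/E.

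- D = 14, E = 120: 19/120 = 15.8%, against 5/120 = 4.2%.
- D = 28, E = 120: 33/120 = 27.5%.
- D = 56, E = 60: start on day 61, end on day 60, duration -1 day.
- A child whose first dose treats a bleed and who then has the 72-hour washout loses at least 72 + 120 = 192 hours, or 8 days.

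**Bleeds lost and ABR.** Simulation inputs: true mean 12 bleeds a year, varying between children (gamma, shape 2); half of bleeds in joints; PK planned uniformly over days 0-14 or 0-28 and postponed until 72 hours after a treated bleed. The switch is uniform over days 14-365 (unrelated to bleeding), or at the third joint bleed if that is earlier. There were 150,000 children per row. ABR = bleeds / days x 365.25.

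| PK day | Switch | Bleeds lost before PK | Mean ABR, SAP clock | Mean ABR, only 120 h removed | Difference | No evaluable episodic period |
|---|---|---|---|---|---|---|
| 0-14 | unrelated | 3.8% | 11.97 | 11.99 | -0.02 | 0.41% |
| 0-14 | third joint bleed | 6.6% | 14.88 | 14.39 | +0.49 | 0.86% |
| 0-28 | unrelated | 7.5% | 11.99 | 11.99 | 0.00 | 2.1% |
| 0-28 | third joint bleed | 12.8% | 15.18 | 14.29 | +0.89 | 3.3% |

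Hand check of the unrelated rows: mean episodic time is (14 + 365)/2 = 189.5 days and mean planned delay is 7 or 14 days. That gives 7/189.5 = 3.7% and 14/189.5 = 7.4%, just under the simulated values because bleeds postpone some visits. In counts, the loss is about 2.4 bleeds (0-14) or 4.7 bleeds (0-28) per 10 episodic starters.

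With PK on day 0, nothing is lost before PK and the two clocks agree (12.1 unrelated, 14.5 third joint bleed; 20,000 children).

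**Sensitivity.**

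- Rates of 6 to 20 a year: 3.6-4.0% lost (unrelated) and 4.5-9.9% (third joint bleed) for days 0-14; 7.5-7.6% and 9.4-17.7% for days 0-28.
- Joint share 0.3 or 0.7 (12 a year, days 0-14, third joint bleed): 5.1% or 8.0% lost; ABR 13.5 against 13.3, or 16.5 against 15.6.
- Rate rising from 0.4 to 1.6 times over a year: ABR 8.8 against 8.6 (unrelated) and 8.7 against 8.4 (third joint bleed) for days 0-14; 9.0 against 8.6 and 9.1 against 8.4 for days 0-28.

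**The case against.** The strongest reply is that little is at stake. The visit is meant to be prompt and may be on the day of screening, the delays above are assumed, and the study is descriptive. That stands. Under the third-joint-bleed switch, most of the inflation comes from ending the period at a bleed. Repairing the clock removes 0.49 of 2.88 above the true 12 (17%), or 0.89 of 3.18 (28%). At 3.3%, at most about one child would lose his episodic period even if all of the roughly 30 enrolled began episodically.

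Several stronger readings are tempting, and the documents do not support them.

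- **A contradiction of the protocol.** Protocol 16.2.1 takes efficacy data from the first study-drug injection, but 16.2.2 leaves the efficacy period to the SAP. This is an unexplained narrowing.
- **A large bias.** With 120 episodic days, PK on day 28, two bleeds before it and one after, the SAP gives 1/87 x 365.25 = 4.20, against 3/120 x 365.25 = 9.13 when all 120 days and all three bleeds count. That rests on an arbitrary split of bleeds; at a constant rate with unrelated switching the mean does not move.
- **Footnote l of Protocol 4.2.1 as proof that such bleeds are expected.** It only says that predose samples are needed from children "who received at least 1 dose of any product containing FIX, including commercially available rFIXFc or a blood product transfusion, prior to the dose". That is a conditional sampling rule, and the sources it names are not study drug. Protocol 7.3.1 is the better support.
- **SAP 5.5 as proof that a missing PK dose is foreseen.** It concerns a missing baseline IR value, which a lost sample would also produce.
- **The prophylaxis start as an inconsistency.** The PK dose equals the recommended weekly prophylactic dose (50 IU/kg), so counting time from it is reasonable there.
- **Data lost to the study.** Listings, exposure days and the inhibitor analysis keep them.

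**Conclusion.** The point holds as a defect in the definition of the efficacy period, with a probably small effect. For episodic starters the rule removes treated and recorded bleeds, time and consumption before a delayed Baseline IR Visit, and it leaves the two cases above without a usable start. How many children are affected is not in the documents.

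The main consequence is lost data: 3.8% to 12.8% of episodic bleeds in the 12-a-year scenarios, and none before the PK dose if that dose is given on the day of enrolment. An upward ABR shift appears only if bleeding prompts the switch or the rate rises with age. In the runs where the ABR moved it was 0.2 to 0.9 a year. The undefined cases need a rule whatever the size, because otherwise they would be settled with open-label data in hand.

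**What to change.** 1. **SAP 5.4.2, efficacy period only.** Start the episodic period at the IXRS enrolment date (00:01 the next day if no time is recorded, as 5.4.2.1 does for episodic re-starts). Add a third adjustment subsection that removes only the interval from the baseline PK dose to 120 hours after it, ending at the first prophylactic dose if that comes sooner. Remove nothing if no PK dose precedes prophylaxis.
2. **SAP 5.3.1.** For the by-regimen safety period (5.4.5) and dosing duration (6.6.1.2), start the episodic regimen at the first study-drug dose. Neither then precedes dosing or overlaps the screening period (5.4.1).
3. **SAP section 10.** State that the episodic efficacy period can begin before the first study-drug injection named in Protocol 16.2.1.

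The first injection should not be the efficacy anchor, because for episodic children it is often itself a bleed. At 12 a year with PK on days 0-14 it gives 12.8 instead of 12.0 (unrelated switch) and 16.6 instead of 14.4 (third joint bleed).

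The cost is a new adjustment rule (5.4.2.2 covers prophylaxis only), separate efficacy and safety starts for episodic children, and a small disclosed departure from Protocol 16.2.1. Where no enrolment time is recorded, a bleed on that day would still fall outside. No visit, dose or data collection changes.
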